11.6.2. Study Population

Demographics and Baseline Data
Age

Only birth year is collected in the eCRF; birth day and month will be imputed as '30th June'.
 
 Birth date will be presented in listings as year of birth, as 'YYYY'. For randomized subjects, age, in whole years, will be calculated with respect to the date of randomization using the imputed date of birth. For subjects not randomized, age, in whole years, will be calculated with respect to the baseline visit date if visit done and date is available, and with respect to screening visit date otherwise.
Duration of Diabetes Disease History

 The duration of diabetes disease history is calculated as the years lapsed between screening visit date and type 2 diabetes diagnosis date. For partial missing diagnosis date, the missing month is imputed as January and the missing day is imputed as the first of the month to calculate duration.
Body Mass Index (BMI)

 Calculated as $\text{Weight (kg)} / [\text{Height (m)}]^2$

Race Groups

 Geographic ancestry data will be combined into categories as provided by the US Food and Drug Administration (FDA) and summarized as FDA race group: 
 American Indian or Alaskan Native Asian (Asian-East Asian Heritage, Asian-Japanese Heritage, Asian-Central/South Asian Heritage, Asian-South East Asian Heritage, Asian-Mixed Race) Black or African American Native Hawaiian or Other Pacific Islander White (White-Arabic/North African Heritage, White-White/Caucasian/European Heritage, White – Mixed Race) Mixed Race (Multiple races are selected, but excludes Asian – Mixed Race and White – Mixed Race) 
Note: Asian – Mixed Race includes subjects who have more than one Asian category selected, but no other categories. White – Mixed Race includes subjects who have more than one White category selected, but no other categories.

Study Treatment Discontinuation, Study Withdrawal, and Follow-up Periods	
Study Treatment Discontinuation	

 • Study Treatment Discontinuation Censored Time (days) = Censoring date – Treatment start date +1 where censoring date is determined as defined for Treatment Stop Date. 	

 • Time to Study Treatment Discontinuation (days) = Treatment stop date – Treatment start date +1 • Study Treatment Person-Years = (Cumulative total of time to treatment discontinuation for subjects who discontinued study treatment + Cumulative total of treatment discontinuation censored time for subjects who did not discontinue study treatment) / 365.25 • Study Treatment Discontinuation Incidence Rate (per 100 person-years) = 100* Number of subjects who discontinued study treatment / study treatment person-years 	
Study Withdrawal	

 • Study Censored Time (days) = Study Completion date (per eCRF Conclusion form) – Randomization date +1 • Time to Study Withdrawal (days) = Study withdrawal date – Randomization date +1 • Study Person-Years = (Cumulative total time to study withdrawal for subjects withdrawing from the study + Cumulative total of study censored time for subjects who did not withdraw from study) / 365.25 • Study Withdrawal Incidence Rate (per 100 person-years) = (100 * Number of subjects who have withdrawn from study) / Study Person-Years 	
Completion Status	

 • Subjects completing study on IP: endpoints will be recorded in the eCRF up until date of final visit during 3 month window. • Subjects completing study off IP: endpoints will be recorded in the eCRF up until date of final subject contact during 3 month window. • Subjects lost to follow-up: efforts to locate and contact subject will continue up until study end. Endpoints will be recorded in the eCRF up until the date of final subject contact (could be after the 3 month window). If endpoint status during or after the 3 month window is obtained then the subject will have completed the study and no further data collection will occur. • Subjects who withdrew consent to contact: collection of information on endpoints will be sought from available sources up until study end. If endpoint status during or after the 3 month window is obtained then the subject will have completed the study and no further data collection will occur. 	
Possible Vital Status Follow-up Time	

 • Possible vital status follow-up time (days) is defined as the following: For subjects who died, use the date of death – randomization date +1 For subjects who did not die, and completed the study, use the Last Study Contact Date – 	

Study Treatment Discontinuation, Study Withdrawal, and Follow-up Periods											

randomization date + 1
 
For subjects who did not die, and did not complete the study, use the date of the middle of the 3 month end of study window (i.e., window start date + floor ((window end date – window start date)/2) – randomization date + 1
											

 • Total possible vital status follow-up time (person years) = Cumulative total of possible vital status follow-up time (days) for all subjects / 365.25 											
Possible CV Follow-up Time											

 • Possible CV follow-up time (days) is defined as the following: For subjects with a first MACE event, use the date of first MACE event – randomization date +1; otherwise use the following: For subjects who died, use the date of death – randomization date +1. For subjects who did not die, and who have an End of Study visit date is within the 3 month end of study window, use the End of Study visit date – randomization date + 1. For subjects who did not die, and whose last visit date is before the beginning of the 3 month end of study window, use the date of the middle of the 3 month end of study window (i.e., window start date + floor ((window end date – window start date)/2) – randomization date + 1). 											

 • Total possible CV follow-up time (person years) = Cumulative total of possible CV follow-up time (days) for all subjects / 365.25 											
Follow-up Periods											

The follow-up periods from the date of randomization associated with event driven analyses are described in the following table. Any endpoints that occurred before randomization are considered to be prior to the time period for follow-up of CV endpoints and will be excluded from all analyses.
											

  
 Endpoint	Follow-up Period	Definition of Follow-Up Period (from date of randomization)	
   
  
 • Primary endpoint (CV death, MI, or Stroke) • Secondary CV Endpoints 	CV Event Assessment [1]	Date of the 1st event or Latest of Last CV assessment date or death date in subjects who had not withdrawn consent^[2]	
 
 All-Cause Mortality	Vital Status Assessment	Date of death or Last study contact date [3]	
  
			Endpoint	Follow-up Period	Definition of Follow-Up Period (from date of randomization)	
 • Primary endpoint (CV death, MI, or Stroke) • Secondary CV Endpoints 	CV Event Assessment [1]	Date of the 1 st event or Latest of Last CV assessment date or death date in subjects who had not withdrawn consent ^[2]	All-Cause Mortality	Vital Status Assessment	Date of death or Last study contact date [3]
Endpoint	Follow-up Period	Definition of Follow-Up Period (from date of randomization)									

 • Primary endpoint (CV death, MI, or Stroke) • Secondary CV Endpoints 	CV Event Assessment [1]	Date of the 1 st event or Latest of Last CV assessment date or death date in subjects who had not withdrawn consent ^[2]									
All-Cause Mortality	Vital Status Assessment	Date of death or Last study contact date [3]									

[1] A sensitivity analysis will be performed to include post-WDC (withdrawal of consent) data (i.e., deaths and CV events if collected through publicly available sources for subjects who have withdrawn consent for all follow-up).
 
[2] Within the time period for follow-up of CV endpoints.
 
[3] Within the time period for follow-up of vital status.
											
Completeness of Follow-up											

For disposition summaries, the completeness of follow-up will be ascertained for CV Event Assessment and Vital Status Assessment through to the End of Study. Definitions are as follows:
											

Study Treatment Discontinuation, Study Withdrawal, and Follow-up Periods

CV Event Assessment: A subject is considered to have complete CV event assessment through to study end if he/she underwent a clinical assessment for CV events at any time during or after the end of study window.

Primary Endpoint Assessment: A subject is considered to have complete primary endpoint assessment if the subject either had complete CV event assessment or experienced a component of the primary endpoint prior to the start of the end of study end visit window.

Vital Status Assessment: A subject is considered to have complete vital status assessment through to study end if he/she has been assessed for vital status at any time during or after the end of study window.

Subjects who have withdrawn consent for all follow-up prior to the start of the end of study visit window and are event free will be considered as having incomplete CV Event and incomplete Primary Endpoint Assessment at study end. However if they experienced a component of the primary endpoint prior to withdrawal of consent they will be considered complete for Primary Endpoint Assessment.

Extent of Exposure

The protocol specifies that subjects start at a dose of 30mg once weekly (albiglutide or albiglutide matching placebo), and that dose increases to 50mg and subsequent dose decreases to 30mg are allowed as deemed appropriate by the Investigator.

Two measures of duration of exposure to study drug will be computed:

- Duration of Exposure Including Breaks = Treatment Stop Date – Treatment Start Date + 1
- Duration of Exposure Excluding Breaks, for which treatment breaks during the study based on eCRF data will be excluded from the overall exposure result. This will be computed as the sum of the durations of exposure determined by the individual entries in the Study Treatment Form.

Based on the eCRF completion guidelines, it is expected that individual entries will be recorded in the Study Treatment Form for breaks of 4 or more consecutive doses, or investigator directed temporary study treatment stoppages. In addition, entries are expected for dose escalations and dose reductions. Consecutive eCRF entries will not describe a break if the start date of the new dose is 10 or less days after the stop date of the previous dose (i.e., (start date – previous stop date) \leq 10).

For albiglutide subjects only, the duration of exposure by dose level will be calculated based on the start and stop dates for each dose level separately.

Duration of exposure in weeks is computed as the corresponding duration of exposure in days divided by 7.

Total Study Treatment Exposure Including Breaks in Person-Years = Cumulative total of (Treatment

Study Treatment Discontinuation, Study Withdrawal, and Follow-up Periods

Stop Date – Start Date + 57) / 365.25

For albiglutide subjects only, Total Study Treatment Exposure Including Breaks in Person-Years will be computed by dose level; this will be done by adding 56 days to the duration of exposure for the latest dose level that was received by the subject.

Example:

Given the following exposure data for an albiglutide subject:

Dose	Start date	Stop date
30mg	SD1	ED1
30mg	SD2 = ED1 + 30	ED2
50mg	SD3 = ED2 + 7	ED3
30mg	SD4 = ED3 + 7	ED4

Duration of Exposure including breaks (weeks):

$$30\text{mg} = [(ED2 - SD1 + 1) + (ED4 - SD4 + 1)] / 7$$

$$50\text{mg} = [ED3 - SD3 + 1] / 7$$

$$\text{Total} = [ED4 - SD1 + 1] / 7$$

Total Study Treatment Exposure Including Breaks (PY):

$$30\text{mg} = [(ED2 - SD1 + 1) + (ED4 - SD4 + 1) + 56] / 365.25$$

$$50\text{mg} = [ED3 - SD3 + 1] / 365.25$$

$$\text{Total} = [ED4 - SD1 + 1 + 56] / 365.25$$

Duration of Exposure excluding breaks (weeks):

$$30\text{mg} = [(ED1 - SD1 + 1) + (ED2 - SD2 + 1) + (ED4 - SD4 + 1)] / 7$$

$$50\text{mg} = [ED3 - SD3 + 1] / 7$$

$$\text{Total} = [(ED1 - SD1 + 1) + (ED2 - SD2 + 1) + (ED3 - SD3 + 1) + (ED4 - SD4 + 1)] / 7$$

Time to first dose escalation and time to first dose reduction are based on start date of study treatment.

Study Treatment Compliance

Two types of study treatment compliance will be computed:

- % Treatment Compliance including breaks =

$$100 * \frac{(\text{Total } \# \text{ pens dispensed} - \text{Total } \# \text{ pens returned unused})}{(\text{Expected } \# \text{ pens used})}$$

Study Treatment Discontinuation, Study Withdrawal, and Follow-up Periods

Expected # pens used = ceiling[Duration of Exposure Including Breaks / 7] where
ceiling [x] = smallest integer \geq x

- % Treatment Compliance excluding breaks =

$$100 * \frac{\text{Total # pens dispensed} - \text{Total # pens returned unused}}{\text{(Sum of Expected # pens used)}}$$

Expected # pens used = ceiling[(stop date – start date + 1) / 7] where
ceiling [x] = smallest integer \geq x. This is computed for each set of start and stop dates recorded in the Study Treatment eCRF form, and then summed up to provide the denominator of the compliance computation.

Categories of treatment compliance will be created as follows: missing, <80%, \geq 80%.

If unused pens are missing/lost and no unused pens are returned, then the number of unused pens returned is expected to be recorded as blank (i.e., missing). If some unused pens are missing/lost but some are returned, then the actual number of unused pens returned is expected to be recorded.

Medication Use

Post-Baseline medications are those with end date on or after the treatment start date or ongoing or missing.

Latest visit medications are those being taken at the latest post-baseline visit (start date on or before latest visit date and end date on or after latest visit date or ongoing or missing).

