11.6. Appendix 6: Derived and Transformed Data

11.6.1. General

Multiple Measurements at One Time Point

- If there are multiple valid records for an assessment within an assigned analysis visit (i.e., assigned by site and/or assigned by slotting), only one of these records will be used for summary statistics and analyses. The record to be used is determined using the following hierarchy (in decreasing order):
 - the record closest to the target visit day
 - the record with an original nominal visit that matches the analysis visit
 - the record earliest in time
 - if the above does not result in a unique record, then the maximum assessment value of the records identified will be used in the determination of summary statistics
- Regardless of the determination of the record to be used for summary statistics, if data are listed, all data will be presented.
- Subjects having both High and Low values for Normal Ranges at any post-baseline visits for safety parameters will be counted in both the High and Low categories of “Any visit post-baseline” row of related summary tables. This will also be applicable to relevant Potential Clinical Importance summary tables.

Randomization Date

- Date subject was randomized as recorded in the eCRF.

Treatment Start Date

- First IP start date

Study Completion/Withdrawal Date

- Date of subject completion or withdrawal is recorded in the eCRF and corresponds to the date of withdrawal for subjects withdrawing from study (date at which the investigator agreed, or determined, that the subject's participation in the study was over; typically, this will be last study visit date) or date of completion of study (last study visit date) for subjects who complete the study (per Section 11.7.1). Subjects who die while on study are considered to have completed the study and completion date is the date of death. For subjects lost to follow-up, the date of withdrawal corresponds to the last contact between the Investigator and the subject during the study period as defined in the protocol.

Treatment Stop Date

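### The completeness-of-follow-up definitions have no clause for death, so known early deaths count as incomplete follow-up in disposition summaries

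*SAP*

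**What the plan says.** The definitions are in SAP section 11.6.2, under Completeness of Follow-up, and are stated to be for disposition summaries.

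- **CV event assessment** is complete "if he/she underwent a clinical assessment for CV events at any time during or after the end of study window".
- **Primary endpoint assessment** is complete "if the subject either had complete CV event assessment or experienced a component of the primary endpoint prior to the start" of the end-of-study window.
- **Vital status** is complete "if he/she has been assessed for vital status at any time during or after the end of study window".
- **One special case** is written out: "Subjects who have withdrawn consent for all follow-up prior to the start of the end of study visit window and are event free" are incomplete for CV event and primary endpoint assessment. If they had a primary endpoint component before withdrawing, they are complete for the primary endpoint.

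Death is treated differently elsewhere in the SAP:

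- Section 11.6.1, Study Completion/Withdrawal Date: "Subjects who die while on study are considered to have completed the study and completion date is the date of death".
- Section 11.6.2, possible vital status and possible CV follow-up time: "For subjects who died, use the date of death". For CV follow-up time this applies when there was no earlier MACE.
- Section 11.6.2, Follow-up Periods table, and section 11.6.3, evaluation period for vital status: for subjects who died, the period ends on the date of death.

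**The concern.** A subject who died before the end-of-study window has the most certain vital status in the trial, yet cannot be assessed alive in or after that window. With no death clause, the written rule puts this subject in the same category as one whose status is unknown. By the other rules of the same document, the subject is a study completer with full possible follow-up.

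Readers use the completeness percentages to judge whether unobserved events could matter to a non-inferiority conclusion. A percentage that falls with each known death is too low. It also depends on outcome: the arm with more deaths appears less well followed even if ascertainment is identical in both arms.

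**Working it through.** **1. Apply the written rules to each kind of death before the window.** Undetermined deaths are analysed as CV deaths (sections 7.1.2 and 11.6.4), so they meet the component clause of the primary endpoint rule.

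| Death before the window | Vital status | CV event assessment | Primary endpoint |
|---|---|---|---|
| CV or undetermined cause | incomplete | incomplete | complete (component) |
| Non-CV, earlier MI or stroke on study | incomplete | incomplete | complete (component) |
| Non-CV, no earlier MI or stroke | incomplete | incomplete | incomplete |

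Under 11.6.1, the follow-up-time rules in 11.6.2 and the vital status period in 11.6.3, subjects in all three rows completed the study and were followed to the end of their possible follow-up. The two sets of rules conflict.

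**2. Size for vital status.** The SAP states no completeness figure to reproduce and no death rate. The planned sample size of about 9400 is from section 1. The share who die before the window is my assumption, varied from 2% to 6%.

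Subjects mislabelled = 9400 × share; highest attainable completeness = 1 − share.

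- 2%: 9400 × 0.02 = 188; ceiling 98%
- 4%: 9400 × 0.04 = 376; ceiling 96%
- 6%: 9400 × 0.06 = 564; ceiling 94%

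**3. Size for the primary endpoint.** Assume further that 20% to 40% of these deaths are non-CV with no earlier MI or stroke.

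- Low end: 188 × 0.20 = 37.6, about 38 subjects; ceiling 1 − 0.02 × 0.20 = 99.6%
- High end: 564 × 0.40 = 225.6, about 226 subjects; ceiling 1 − 0.06 × 0.40 = 97.6%

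**4. Difference between arms.** Assume equal arms and a mortality ratio of 1.2. If the overall share is d, the arms have d/1.1 and 1.2d/1.1, a difference of 0.2d/1.1.

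- d = 2%: 0.36 percentage points
- d = 6%: 1.09 percentage points

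This is the artificial gap in displayed vital status completeness. For the primary endpoint, if the same ratio holds for the relevant non-CV deaths, it is 0.36 × 0.20 = 0.07 to 1.09 × 0.40 = 0.44 points.

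**5. What does not move.** The event target reproduces: 4 × (1.960 + 1.282)² / (ln 1.3)² gives 611 events for 90% power. It does not use these definitions. In section 11.6.4 the CV follow-up period ends at the later of the Last CV Assessment Date and the death date, for subjects who had not withdrawn consent or reached the End of Study. Censoring in the primary analysis is therefore independent of them.

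**The case against.** The strongest reply is that a recorded death obviously settles vital status through to study end. The Follow-up Periods table, just above the definitions, already ends the mortality period at death, and a sensible programmer would classify deaths correctly. The table shells are not in the SAP, so it cannot be shown that any display would be wrong. Tables 1.09, 1.10 and 1.16 and Figure 1.03 look from their titles like the places where the definitions would be used, but that is an inference.

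Part of this stands: the problem lies in the written rule and is not a demonstrated wrong output. But the authors did write exceptions here, for an earlier primary endpoint component and for withdrawal of consent, and wrote none for death. A literal derivation compares an assessment date with the window start and flags early deaths as incomplete. The lenient reading is weakest for the primary endpoint rule, whose only alternative route is a component event, which a non-CV death is not.

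Two stronger readings are not supported. A reader might infer that the number of truly missing outcomes is hidden. It is not: survival status (Table 1.09), adjudicated cause of death (Table 2.35) and time to death (Table 3.001) are reported separately, so known deaths can be set apart. A reader might also infer that every death on study is affected. A death inside the window can be taken as status established in the window, so a count based on all deaths over all follow-up would be too high.

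**Conclusion.** The concern holds as a minor error in the definitions. As written, every known death before the end-of-study window is incomplete for vital status and CV event assessment. Non-CV deaths without an earlier MI or stroke are also incomplete for the primary endpoint. This contradicts the SAP's own treatment of death as completion and as the end of follow-up.

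Under the assumed 2% to 6% of deaths before the window, 188 to 564 subjects with known vital status would be mislabelled. About 38 to 226 would be mislabelled for the primary endpoint if 20% to 40% of those deaths are of the relevant non-CV kind. None of these rates comes from the SAP.

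It would be tempting to conclude that the non-inferiority result is put at risk. The document does not support that. The definitions are confined to disposition summaries, and the hazard ratio, its confidence interval and the censoring rules do not use them. The tipping-point analysis refers to study non-completers, and section 11.6.1 counts subjects who die on study as completers.

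**What to change.** Add to Completeness of Follow-up in section 11.6.2:

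- A subject known to have died before or during the end-of-study window has complete vital status assessment.
- A subject who died of any cause, with CV event status established up to death, has complete CV event assessment and complete primary endpoint assessment.

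The condition in the second sentence matters. A subject who withdrew consent or was lost, and was later found to have died, should be complete for vital status but not automatically for CV events. The SAP should state how status up to death is judged. Apply the rule to whichever disposition and follow-up displays use these definitions.

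The cost is one or two sentences and a small change to a derivation. No new data are needed, and no event count, sample size or power changes.

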11.2.1. Time and Events Table

Procedures ^{1,2}	Screening ³	Randomization ³ /Baseline (can be same day as Screening Visit)	Study Drug Check Phone Call (4-6 wks post rand.)	Clinic Visit Month 4 ± 18 days then every 4 months ± 18 days throughout the study	Unscheduled dose adjustment visit (if warranted)	Final study clinic visit ⁴ (or early withdrawal)	Follow up Phone Call 5 ± 1 weeks after last IP dose
Written informed consent	X						
Review of Inc/excl criteria	X	X					
Demography & directed medical history	X						
Assessment of MACE and micro-vascular events				X		X	
HbA1c	X ⁵			X		X	
Serum creatinine (eGFR)	X ⁵			X (alternate visits) ²		X	
Liver Function Tests (LFTs) ⁶		X		X (alternate visits) ²		X	
Record available information on most recent lipid assessment ⁷		X		X (annually)		X	
Genetic sampling ⁸		X					
Patient reported outcomes questionnaires ⁹		X ¹⁰		X (alternate visits) ²		X	
Key concomitant non-diabetes medication		X		X		X	X
Diabetes medication		X		X		X	X
Study drug reminder			X	X	X		
Physical examination ¹¹		X		X (alternate visits) ²		X	
SAEs, AEs of special interest, AEs leading to IP discontinuation		X	X	X	X	X	X
Pregnancy test ¹²	X	X					
Study drug dispense/compliance ¹³		X		X	X	X	

1. Subjects who discontinue investigational product should be handled as described in Protocol Section 4.4 and Section 4.5. and Table 2 .
2. Assessments at month 8, 16, 24 etc. will include patient reported outcomes questionnaires, serum creatinine (eGFR), LFTs and physical examination. Those at months 4, 12, 20 etc do not.
3. Screening and Randomization can occur at the same visit if all eligibility information is available. If Screening and Randomization occur at the same visit assessments should not be duplicated.
4. Once it is projected that the target number of MACE events will have been collected, a 3 month window will be defined for conducting the final, face to face visit.

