The start date of the time period for capturing On-therapy deaths is the treatment start date for subjects who received study treatment, and the date of randomization otherwise. The end of this time period is defined as follows: 
 For subjects who did not receive study treatment, use the date of randomization. For all subjects known to have died, use the earliest of the following two dates: treatment stop date + 56 days and date of death. Otherwise, use the earliest of the following two dates: treatment stop date + 56 days and Last Study Contact Date. If the censoring date as defined above for On-therapy deaths is after the censoring date as defined for the time period for follow-up of vital status, then use the censoring date as defined for the time period for follow-up of vital status. Any events that occurred before the start of this time period are considered to be prior to the time period for On-therapy deaths, and any events that occurred after the end of this time period are considered to be post the time period for On-therapy deaths.

 Endpoint person-years = (cumulative total time to death for subjects who died + cumulative total of censored time for subjects without the event) / 365.25 Incidence rate (per 100 person-years) = (100 * number of subjects who died) / endpoint person-years Endpoint absolute rate difference (per 100 person-years) = albiglutide incidence rate (per 100

Time to Death endpoint

person-years) – placebo incidence rate (per 100 person-years)

Adverse Events

General definitions

- Time to first AE is defined as follows:
For subjects who had at least one AE of interest, time to first AE = onset date of first AE – treatment start date + 1.
For subjects who did not have at least one AE of interest, time to first AE (censored) is the censoring date – treatment start date + 1.
Censoring date will be assigned based on the evaluation time period of interest as subsequently specified.
- AE incidence rate (per 100 person-years) = $(100 * \text{number of subjects with at least one AE}) / \text{first AE person-years}$
- First AE person-years = $(\text{Cumulative total of time to first AE for subjects who have the AE} + \text{Cumulative total of censoring time for subjects without the AE}) / 365.25$

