- AE density, also referred to as event density, will be calculated for specified AEs. AE density = number of events / AE density person-years and will be presented per 100 person-years.
- AE density person-years = cumulative total of censoring time / 365.25, where censoring time is the censoring date – treatment start date + 1. Censoring date will be assigned based on the evaluation time period of interest as subsequently specified.

Time Period for On-treatment AEs

The time period for capturing On-treatment AEs begins at treatment start date. The end of this time period is the earliest of the following two dates: treatment stop date, latest of clinic visits, phone calls and other contact with subject.

Any events that occurred before the start of this time period are considered to be prior to the time period for On-treatment AEs, and any events that occurred after the end of this time period are considered to be post the time period for On-treatment AEs.

Time Period for On-therapy AEs

The time period for capturing On-therapy AEs begins at treatment start date. The end of this time period is the earliest of the following two dates: treatment stop date + 56 days and latest of clinic visits, phone calls and other contact with subject.

Any events that occurred before the start of this time period are considered to be prior to the time period for On-therapy AEs, and any events that occurred after the end of this time period are considered to be post the time period for On-therapy AEs.

Time Period for On-therapy and Post-therapy AEs
--

The time period for capturing On-therapy and Post-therapy AEs begins at treatment start date. The

end of this time period is the latest of the following: latest of clinic visits, phone calls and other contact with subject, latest non-missing AE start date, latest non-missing AE end date.

Any events that occurred before the start of this time period are considered to be prior to the time period for On-therapy and Post-therapy AEs, and any events that occurred after the end of this time period are considered to be post the time period for On-therapy and Post-therapy AEs.

AEs of Special Interest

Following are the protocol-specified AEs of special interest:

- Development of thyroid cancer
- Haematologic malignancy
- Pancreatic cancer
- Pancreatitis
- Investigational Product Injection site reactions
- Immunological reactions
- Severe hypoglycaemic events
- Hepatic events
- Hepatic enzyme elevations (including GGT)

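### Exposure definitions are inconsistent: total person-years add 56 days even after death or last contact, and the excluding-breaks duration drops dose-change intervals that the SAP says are not breaks

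*SAP*

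**What the plan says.** SAP section 11.6.2, under Extent of Exposure, gives three measures.

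- Duration including breaks: "Duration of Exposure Including Breaks = Treatment Stop Date – Treatment Start Date + 1".
- Duration excluding breaks: "This will be computed as the sum of the durations of exposure determined by the individual entries in the Study Treatment Form". The same block adds a rule on what counts as a break: "Consecutive eCRF entries will not describe a break if the start date of the new dose is 10 or less days after" the previous stop date.
- Total exposure including breaks, in person-years: the sum over subjects of "Stop Date – Start Date + 57) / 365.25". By dose level, for albiglutide only, "this will be done by adding 56 days to the duration of exposure for the latest dose level that was received by the subject".

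A worked example follows: two 30 mg entries, then 50 mg, then 30 mg, with SD2 = ED1 + 30, SD3 = ED2 + 7 and SD4 = ED3 + 7.

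Section 11.6.3 uses the same window of stop date plus 56 days, but limits it. For On-therapy deaths, in subjects who died: "use the earliest of the following two dates: treatment stop date + 56 days and date of death". For other subjects the second limit is the last study contact. The On-therapy adverse event period ends at the earlier of "treatment stop date + 56 days and latest of clinic visits, phone calls and other contact with subject". Section 11.6.4 limits the On-therapy CV period at the last CV assessment or death. The schedule in section 11.2.1 has as its last column "Follow up Phone Call 5 ± 1 weeks after last IP dose".

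**The concern.** The 56-day tail is the plan's declared On-therapy window, and counting it as exposed time is a legitimate choice. The difficulty is that only the exposure total lets the window run past the end of the subject's life or observation. A subject who dies the day after the last dose is credited with 55 days of exposure after death. One report would then carry two different person-year totals for the same subjects and the same nominal window: one in the exposure summary, one behind the On-therapy adverse event densities.

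The excluding-breaks measure has a different fault. The 10-day rule and the instruction to sum entries give different answers whenever a dose changes on the normal weekly interval. The example follows the sum, so the 10-day rule has no effect there. A programmer could follow either and report different durations.

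**Working it through.** **Inputs.** About 9400 subjects (SAP sections 1 and 2.3). The 56-day tail, the 10-day rule and the worked example (section 11.6.2). Final call 5 ± 1 weeks after the last dose, i.e. 28 to 42 days (section 11.2.1). Assumptions, because the SAP gives no figures: 60–90% of subjects complete on drug; their final call is their last contact; mean treatment time is 1.2–1.4 years.

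**The SAP's own formulas.** 57 = 1 + 56, so the person-years formula is the including-breaks duration plus 56 days. The example total, [ED4 − SD1 + 1 + 56]/365.25, follows from it. The example's excluding-breaks total is the sum of its four entries. Both reproduce.

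**Size of the tail**
- Per subject: 56/365.25 = 0.153 person-years.
- All subjects, at most: 9400 × 56/365.25 = 1441 person-years.
- Unobserved days in a subject completing on drug: 56 − 42 = 14 to 56 − 28 = 28.
- Low: 9400 × 0.60 × 14/365.25 = 216 person-years.
- Middle (75%, call at 35 days): 9400 × 0.75 × 21/365.25 = 405.
- High: 9400 × 0.90 × 28/365.25 = 649.
- The middle value as a share of the SAP's total, tail included: 405/(9400 × 1.553) = 2.8% to 405/(9400 × 1.353) = 3.2%.

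Each death on drug adds up to 56 further days.

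**Excluding breaks, in the worked example**
- Days between entries: SD2 − ED1 − 1 = 29; SD3 − ED2 − 1 = 6; SD4 − ED3 − 1 = 6.
- Summing entries removes 29 + 6 + 6 = 41 days from the including-breaks duration.
- Under the 10-day rule only the 30-day interval is a break, so 29 days should go.
- Difference: 12 days, whatever the entry lengths.

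With illustrative entries of 113, 113, 169 and 113 days, the including-breaks duration is 508 + 41 = 549 days. Summing entries gives 508; the 10-day rule gives 549 − 29 = 520.

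**Dose levels, including breaks**
- 30 mg = (ED2 − SD1 + 1) + (ED4 − SD4 + 1) = 255 + 113 = 368 days.
- 50 mg = ED3 − SD3 + 1 = 169 days.
- Sum = 537, against a stated total of 549.

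The same 12 days are missing. The 29-day break counts as 30 mg exposure, while the two 6-day dose-change intervals count at neither dose.

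**The case against.** The strongest reply is that nothing inferential depends on this. Adverse event incidence and density, deaths and first CV events each have their own person-years (sections 11.6.3 and 11.6.4), and the primary Cox model does not use exposure. Durations in weeks carry no tail, so the untailed figure is reported as well. Subjects who stop treatment early stay on scheduled follow-up, so their 56 days are mostly observed. All of this stands, and it limits the point to a descriptive table and figure.

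A reader might infer more than the document supports:

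- *That the SAP states wrong exposure figures.* It states none, and its example agrees with its literal formulas. The fault lies in the definitions.
- *That all 1441 person-years are spurious.* That is the whole tail; under the assumptions above, most of it is observed.
- *That ordinary weekly dosing intervals are removed.* Intervals within an eCRF entry are counted. Days are lost only between entries, which arise for dose changes, longer breaks and directed stoppages.
- *That the arms are affected differently.* Dose changes might differ by arm, but the SAP gives nothing that shows it.

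A further objection concerns the repair. A plain minimum with the latest contact could delete real dosing time. Clinic visits are 4-monthly, so a subject who doses for 90 days after the last contact and then dies would lose about 90 days of actual exposure. That is correct, and any limit must allow for it.

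**Conclusion.** Both inconsistencies are in the SAP text. Followed as written, section 11.6.2 counts time after death or last contact as exposure and treats intervals as excluded that its own rule says are not breaks.

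The unobserved exposure is about 216 to 649 person-years, 405 in the middle case. These values rest on the assumed completion share and last-contact timing; the percentage also rests on the assumed treatment time. Deaths on drug come on top. The excluding-breaks loss needs no such assumption: 6 days per dose change at a 7-day interval, 12 days in the example.

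This is a definition and consistency fault confined to the exposure summary (Table 1.49) and, for excluding breaks, Figure 1.05. The change is worth making because it is cheap, not because any efficacy or safety rate is at risk.

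**What to change.** 1. **Limit the tail.** For subjects who died, end exposure at min(stop + 56 days, death date). For others, end it at min(stop + 56 days, latest contact), but never before the treatment stop date. Person-years are then (end − start + 1)/365.25. Apply the same limit to the tail added to the latest dose level.
2. **Merge before summing.** Treat entries 10 or fewer days apart as continuous in the excluding-breaks duration. The example's total becomes [(ED1 − SD1 + 1) + (ED4 − SD2 + 1)]/7; with the illustrative lengths, (113 + 407)/7 = 520/7 weeks.
3. **Assign the dose-change interval to one dose level**, for example the preceding one, and correct both parts of the example so that the levels add up. With the illustrative lengths, including breaks: 30 mg = 255 + 6 + 113 = 374, 50 mg = 169 + 6 = 175, total 549. Excluding breaks: 30 mg = 113 + 119 + 113 = 345, 50 mg = 175, total 520.

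The cost is SAP wording and derivation code, using dates the SAP already derives. The downside is a slightly smaller total of person-years.
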